#### 6.1.1. Imputation on Start / End Date of Adverse Events

Partial start/end dates for any adverse events will be imputed using the following convention.

For start date of adverse events,

1. Day Missing— impute with the first day of the month. If both month and year

are the same as those of the first dose administration in double-blind treatment period, then impute with the first dose administration date in double-blind treatment period.

2. Day and Month Missing – impute with January 1st. If year is the same as that of the first dosing in double-blind treatment period, then impute with the first dosing date in double-blind treatment period.
3. Completely Missing - impute with the first dose administration date in double-blind treatment period. If end time of adverse event is earlier than the date of the first dose administration in double-blind treatment period, then impute with the date of informed consent form.

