#### End date of adverse events

1. Day Missing – impute with the last day of the month. If both month and year are the same as those of date withdrawn from study, then impute with the date withdrawn from study.
2. Day and Month Missing – impute with December 31st. If year is the same as that of date withdrawn from study, then impute with the date withdrawn from study.
3. Completely missing – if the adverse event is on-going then no imputation will be applied. If an adverse event ends, then impute with the date withdrawn from study. Furthermore, if the subject hasn't withdrawn from study in double-blind treatment period analyses, then impute with the cut-off date of double-blind treatment period analyses.

Imputation for start / end date of adverse events will be applied to determine treatment emergent adverse event only. It will not be used in other analyses, such as calculating the duration of adverse events.

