#### **6.1.2. Imputation on Start / End Date of Concomitant Medications**

When start date of concomitant medicine is missing, the following convention will be applied.

1. Day Missing – impute with the first day of the month. If both month and year are the same as those of the first dose administration in double-blind treatment period, then impute with the first dose administration in double-blind treatment period.
2. Day and Month Missing – impute with January 1st. If year is the same as that of the first dose administration in double-blind treatment period then impute

with the first dose administration date in double-blind treatment period.

3. Completely Missing - impute with the first dose administration date in double-blind treatment period. If end time of concomitant medicine is earlier than the date of informed consent form, then impute with the date of informed consent form. If end date of concomitant medicine is earlier than date of informed consent form then no imputation will be applied and it will be determined as prior run-in concomitant medicine.

When end date of concomitant medicine is missing, impute following below rules.

1. Day Missing – impute with the last day of the month. If both month and year are the same as those of date withdrawn from study, then impute with the date withdrawn from study.
2. Day and Month Missing – impute with December 31st. If year is the same as that of date withdrawn from study, then impute with the date withdrawn from study.
3. Completely Missing – if the concomitant medicine is on-going then no imputation will be made. If an adverse event ends, then impute with the date withdrawn from study.

Imputation of start / end date concomitant medicine will be applied to determine the concomitant medicine in prior run-in, run-in and treatment period only. It will not be used in other analyses, such as calculating the duration of dosing.

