### 9.3.2. Adverse Events

Adverse events will be coded using MedDRA version 22.0.

Adverse events start before the first exposure to study treatment in double-blind treatment period will be included in the listing of all adverse events.

Treatment emergent adverse events (TEAEs) will be summarized for double-blind period and open-label period respectively. TEAEs are defined as any adverse event present after the first exposure to study treatment or any already presented events that worsened after the first exposure to study treatment.

TEAEs in double-blind treatment period: any adverse event present after the first exposure to study treatment or any already presented events before first double-blind dose administration that worsened after the first exposure to study treatment till the end of double-blind treatment period.

Treatment related adverse events: Adverse events that “Related” or “Probably related” to study treatments.

Important Adverse events: any adverse events, except serious adverse events, leads to results in actions of medical treatment (such as dose discontinuation, dose reducing or symptomatic approach treatment) and abnormal hematological or other lab test results.

Incidence rate of adverse events, treatment related adverse events, serious adverse events and adverse events result in withdrawal from study will be summarized and counted by SOC/PT for each treatment group. The frequency of AEs will be counted for each subject only once per PT name. The difference incidence rate between treatment groups will be compared using Fisher’s Exact test.

Adverse Events will be summarized by severities, if an adverse event occurs more than once on a given subject, then the worst will be counted.

Adverse events with incidence rate  $\geq 2\%$  and  $\geq 5\%$  will be summarized by PT name.

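### SAP 6.1.1 checks an AE's end date only when its start is wholly missing, so a resolved run-in AE with a partial start can be dated after its own end and counted as treatment-emergent

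*Supplement*

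**What the plan says.** SAP 6.1.1 gives three rules for an incomplete AE start date.

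- **Rule 1, day missing.** Use the first of the month, unless month and year "are the same as those of the first dose administration in double-blind treatment period, then impute with the first dose administration date".
- **Rule 2, day and month missing.** Use 1 January, with the exception: "If year is the same as that of the first dosing in double-blind treatment period, then impute with the first dosing date".
- **Rule 3, completely missing.** Use the first double-blind dose date, with one safeguard: "If end time of adverse event is earlier than the date of the first dose administration in double-blind treatment period", the consent date is used instead.

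The section limits what these dates are for: "Imputation for start / end date of adverse events will be applied to determine treatment emergent adverse event only".

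SAP 9.3.2 then says "TEAEs are defined as any adverse event present after the first exposure to study treatment", or an existing event that worsens after it. It also says "Adverse events start before the first exposure to study treatment in double-blind treatment period will be included in the listing of all adverse events".

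Protocol v1.1, section 7.2.2, collects non-serious AEs from the first run-in dose, and note 1 to its Schedule of Assessments starts the run-in at Day -28 (±3 days). Resolved pre-treatment AEs will therefore be in the database.

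SAP 6.1.2 has parallel rules for concomitant medications. Its rules 1 and 2 also lack an end-date check. Its rule 3 checks the end only against consent: "If end time of concomitant medicine is earlier than the date of informed consent form, then impute with the date of informed consent form". The next sentence, for the same condition, says not to impute and to class the medication as prior to run-in.

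**The concern.** Dating an event of uncertain onset to treatment is a reasonable conservative default. It stops being reasonable when the recorded end date shows that the event was over before the first double-blind dose. The authors saw this, because they wrote the safeguard into rule 3. As drafted, though, it protects only the AE with the least start information. An AE whose start month is known is handled worse than one whose start is not known at all.

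At stake is the accuracy of the TEAE tables: placebo run-in events that resolved before randomized treatment could be reported as emerging on it. In 6.1.2, a medication that stopped during run-in and has no start date is placed at the first double-blind dose, after it had stopped. Those dates decide which period's medication table it enters.

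**Working it through.** The plan states no figure on this point, so there is none to reproduce. The check applies the rules as written, then asks how often their trigger is met.

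**Step 1. Worked example** (dates assumed): consent 10 May 2018, first double-blind dose 20 June 2018, AE end 10 June 2018.

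| Recorded start | Rule | Start as written | After end? | TEAE by start? | Start with check extended |
|---|---|---|---|---|---|
| June 2018, day missing | 1 | 20 June | yes | yes | 1 June |
| May 2018, day missing | 1 | 1 May | no | no | 10 May |
| 2018, day and month missing | 2 | 20 June | yes | yes | 10 May |
| completely missing | 3 | 10 May | no | no | 10 May |

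The fault needs both a match between the known part of the start and the first dose, and a recorded end before that dose. With the check extended, no start falls after the end and no row is a TEAE.

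**Step 2. How often the known part matches.** Assume the first dose is uniform over a 365-day year and AE onset is uniform over Days -28 to -1. That gives 365 × 28 = 10,220 combinations.

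- Same calendar month and year as the first dose (rule 1): 5,348 / 10,220 = 52%.
- Same year (rule 2): onset falls in the previous year only when the first dose is on 1 to 28 January, which is 28 + 27 + … + 1 = 406 combinations. (10,220 − 406) / 10,220 = 96%.

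**Step 3. Add that the AE ended before the first dose.** With duration D = end − start + 1 (SAP 6.2), an AE starting L days before the dose has ended before it when L ≥ D.

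| Duration (assumed) | Rule 1: start after end | Rule 2: start after end |
|---|---|---|
| 3 days | 4,654 / 10,220 = 46% | 9,087 / 10,220 = 89% |
| 5 days | 4,008 / 10,220 = 39% | 8,364 / 10,220 = 82% |
| 7 days | 3,410 / 10,220 = 33% | 7,645 / 10,220 = 75% |

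The denominator is run-in AEs that already have a partial start of that type and a known end. It is not all AEs, nor all run-in AEs.

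**Step 4. The 6.1.2 consent conflict.** Consent is at Visit 1 (Day -42 to -29), before run-in. For a medication that ended before consent, imputing the consent date gives prior to run-in by start date (SAP 7.4, Definition 1). Not imputing gives prior to run-in by direct instruction. The class is the same, so the conflict is one of wording. The medication that ended during run-in with no start date is different: rule 3 dates it to the first double-blind dose, and Definition 1 puts it in the treatment period.

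**The case against.** The strongest objection is that the SAP does not strictly compel a TEAE. Its definition speaks of events present after first exposure, and an AE with a recorded end ten days before dosing was not. Section 6.1.1 also imputes end dates for the TEAE decision, which would serve little purpose if only the start counted. This has some force, so misclassification is not certain. It does not remove the fault. No end-date condition for TEAEs is written anywhere, 9.3.2 separates pre-treatment events by start, and rule 3 shows that the authors thought the check was needed. A programmer who follows rules 1 and 2 literally gets a start after the end and a TEAE.

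The second objection is that the case will be rare, and this stands. Subjects keep AE diaries, Visits 2, 3 and 4 span the run-in, start and end dates are collected for each AE (protocol 7.2.3), and discrepancies go back to the investigator (protocol 8.4). A start with day and month both missing but a known end, inside about 28 days, is hard to imagine often.

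Two stronger readings are tempting and unsupported. The 2:1 allocation might suggest that false events load onto HMS5552. It affects counts only: the events occur on placebo before randomization, so the expected proportion is equal in the arms, and 9.3.2 compares incidence rates. A reader might also take 39% or 82% as the share of AEs misreported; these are conditional on a subgroup whose size is unknown.

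**Conclusion.** The point holds as a drafting fault in SAP 6.1.1, rules 1 and 2. They can give an AE a start later than its recorded end, and sorting by start would then make a resolved run-in event treatment-emergent. The expected consequence is a slight inflation of TEAE incidence in both arms, without expected between-arm bias. Its absolute size cannot be computed, because the number of partial dates is not given. The conditional shares rest on uniform dosing dates and onsets, durations of 3 to 7 days and known end dates.

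No efficacy analysis is touched. In 6.1.2 the substantive gap is the medication that ended before the first double-blind dose but is dated to or after it. A reader might infer that the contradictory consent instructions change its classification; they do not, though only one of them should stay. The correction is worth making because it is cheap and completes a safeguard that the SAP already contains.

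**What to change.** **SAP 6.1.1.** Place the end-date check ahead of all three start-date rules. If the recorded end date, complete or partial, shows that the AE ended before the first double-blind dose, impute the earliest date consistent with the recorded part of the start, not earlier than informed consent, and do not classify the event as a TEAE. Otherwise rules 1 to 3 apply as now, so events of unknown end stay assigned to treatment.

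**SAP 6.1.2.** If the recorded end precedes the first double-blind dose, do not impute a start after that end.

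- *Partial start:* use the earliest date consistent with the recorded part, with no consent-date floor. Medications often begin before consent, and a floor would override a recorded earlier year.
- *Completely missing start:* classify by the recorded end. If it ended before consent, do not impute and class it as prior to run-in; keep that instruction and delete the one that imputes the consent date. If it ended after consent but before the first double-blind dose, do not assign it to the treatment period.

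**Cost.** A few sentences in two SAP sections and a small change to the date derivations, made before unblinding. No new data are needed.

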#### End date of adverse events

1. Day Missing – impute with the last day of the month. If both month and year are the same as those of date withdrawn from study, then impute with the date withdrawn from study.
2. Day and Month Missing – impute with December 31st. If year is the same as that of date withdrawn from study, then impute with the date withdrawn from study.
3. Completely missing – if the adverse event is on-going then no imputation will be applied. If an adverse event ends, then impute with the date withdrawn from study. Furthermore, if the subject hasn't withdrawn from study in double-blind treatment period analyses, then impute with the cut-off date of double-blind treatment period analyses.

Imputation for start / end date of adverse events will be applied to determine treatment emergent adverse event only. It will not be used in other analyses, such as calculating the duration of adverse events.

#### **6.1.2. Imputation on Start / End Date of Concomitant Medications**

When start date of concomitant medicine is missing, the following convention will be applied.

1. Day Missing – impute with the first day of the month. If both month and year are the same as those of the first dose administration in double-blind treatment period, then impute with the first dose administration in double-blind treatment period.
2. Day and Month Missing – impute with January 1st. If year is the same as that of the first dose administration in double-blind treatment period then impute

with the first dose administration date in double-blind treatment period.

3. Completely Missing - impute with the first dose administration date in double-blind treatment period. If end time of concomitant medicine is earlier than the date of informed consent form, then impute with the date of informed consent form. If end date of concomitant medicine is earlier than date of informed consent form then no imputation will be applied and it will be determined as prior run-in concomitant medicine.

When end date of concomitant medicine is missing, impute following below rules.

1. Day Missing – impute with the last day of the month. If both month and year are the same as those of date withdrawn from study, then impute with the date withdrawn from study.
2. Day and Month Missing – impute with December 31st. If year is the same as that of date withdrawn from study, then impute with the date withdrawn from study.
3. Completely Missing – if the concomitant medicine is on-going then no imputation will be made. If an adverse event ends, then impute with the date withdrawn from study.

Imputation of start / end date concomitant medicine will be applied to determine the concomitant medicine in prior run-in, run-in and treatment period only. It will not be used in other analyses, such as calculating the duration of dosing.

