### **Exceptions for Target Disease**

1. The T2DM medical history is more than 3 years when signing the informed consent form.
2. Treated with any antidiabetic drugs for more than 14 days within 3 years or treated with any antidiabetic drugs within 3 months before screening.
3. History of severe hypoglycemia (requiring external assistance for recovery) or recurrent hypoglycemia (such as experience of 3 or more times of hypoglycemia  $\leq 3.9 \text{ mmol/L}$  or hypoglycemia symptoms within 1 month) without contributing factors within 3 months before screening.
4. Fasting C-peptide  $< 1.0 \text{ ng/ml}$  at screening (round original values to 1 decimal place).
5. Medical history of diabetic ketoacidosis, diabetes lactic acidosis or hyperosmotic nonketotic diabetic coma.
6. Clinically diagnosed type 1 diabetes mellitus, diabetes mellitus induced by pancreatic injury or other special types of diabetes mellitus.

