## 6. General Conventions For Data Handling

### 6.1. Premature Withdraw and Missing Data

In FAS, missing data will be imputed by LOCF method for ANCOVA. Missing values will be imputed with the last non-missing available on-treatment assessment (including unscheduled visit). If categorical parameter is derived with quantitative parameters, the derivation will be conducted after missing data imputation of quantitative parameter is completed.

When month and day of birth date are missing, then “July” and “15th” will be used to impute the missing month and missing day respectively. Same imputation rule will be used to impute the missing initial diagnosis date of type II diabetes.

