### **7.4. Prior and Concomitant Medication**

Concomitant treatment will be coded using the World Health Organization (WHO) Drug dictionary and be summarized by ATC level 4 and preferred term. If ATC level 4 is missing, then it will be imputed with level 3. If ATC level 3 is missing, then it will be imputed with level 2. Concomitant medications will be summarized for prior to run-in period, during run-in period and during treatment period. Concomitant medications will be summarized following rules below.

Definition 1: According to the start date of concomitant medication prior to run-in period, during run-in period and during treatment period, it will be classified as concomitant medication prior to run-in period, concomitant medication during run-in period and concomitant medication during treatment period.

Definition 2: Concomitant medications will be determined by start/end time of concomitant medications. Once exposed to concomitant medications during prior run-in period, run-in period and treatment period then those concomitant medications will be summarized in corresponding periods. For example, if the start date of one concomitant medication is in run-in period and the end date is also in run-in period, then the concomitant medication will only be summarized in run-in period. If the start date of one concomitant medication is in run-in period and the end date is in treatment period, then the concomitant medication will be summarized in run-in period and treatment period.

When start date and end date of concomitant medications are missing, please refer to [Section 6.1.2](#) for imputation rules.

Usage of all concomitant medications will be listed based on randomized analysis set.

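### SAP 6.1.2 and 6.1 contain date-imputation rules that can start a medicine after it ended and date a diabetes diagnosis after consent; descriptive tables only

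*Supplement*

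**What the plan says.** **Medicines (SAP 6.1.2, start date, item 3).** The default is "Completely Missing - impute with the first dose administration date in double-blind treatment period". Two consecutive sentences then deal with a medicine that ended before consent. The first reads "If end time of concomitant medicine is earlier than the date of informed consent form, then impute with the date of informed consent form"; the second reads "If end date of concomitant medicine is earlier than date of informed consent form then no imputation will be applied" and classes the medicine as prior to run-in. Section 6.1.2 restricts the use of these dates: they "will be applied to determine the concomitant medicine in prior run-in, run-in and treatment period only". In SAP 7.4, Definition 1 sorts by start date alone ("it will be classified as concomitant medication prior to run-in period, concomitant medication during run-in period and concomitant medication during treatment period"). Definition 2 uses start and end, and counts a medicine in every period in which it was taken.

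**Adverse events (SAP 6.1.1, start date, item 3).** The parallel rule has the same default but a different exception: "If end time of adverse event is earlier than the date of the first dose administration in double-blind treatment period", the consent date is used.

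**Diabetes diagnosis (SAP 6.1 and 6.2).** A missing birth month becomes July and a missing birth day the 15th. SAP 6.1 then adds: "Same imputation rule will be used to impute the missing initial diagnosis date of type II diabetes". SAP 6.2 computes duration in months as (consent date - diagnosis date + 1)/30.4375. Protocol v1.1, section 4.2, excludes a subject if "The T2DM medical history is more than 3 years when signing the informed consent form". Section 4.1 asks for at least 3 months of diet and exercise before entry.

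**The concern.** A date rule should never produce an order of events that cannot have happened. The medicines rule does so for a foreseeable case, a medicine stopped during screening or run-in. Assigning medicines to periods is the only purpose of these imputed dates, so a wrong period is an error in the one thing the rule is for. The two sentences on an end before consent also leave the programmer to choose between them.

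The mid-year convention is harmless for a birth date decades back. It is not harmless for a disease that began at most 3 years before consent, where a shift of several months can move the diagnosis past consent or outside the eligibility limit. At stake are the by-period medication tables and the baseline summary of disease duration.

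**Working it through.** The documents give no figure to reproduce, so the rules are applied literally to dates.

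**1. Medicines.** Protocol 3.5.1 puts screening at Day -42 to -29, and 3.5.2 starts run-in at Day -28 ± 3. Illustrative dates (assumed): consent 1 April 2018 (Day -42), run-in from 15 April, first double-blind dose 13 May. The start date is completely missing.

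| Recorded end | Imputed start under 6.1.2 | Start minus end |
|---|---|---|
| 1 March, before consent, first sentence | 1 April (consent) | +31 days |
| 1 March, before consent, second sentence | none; prior to run-in | not applicable |
| 10 April, after consent, before run-in | 13 May | +33 days |
| 25 April, in run-in | 13 May | +18 days |
| 12 May, in run-in | 13 May | +1 day |
| 1 June, on treatment | 13 May | -19 days (possible) |

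- The 10 April, 25 April and 12 May rows meet neither exception, because both exceptions require an end before consent. Definition 1 files all three as started during treatment. Under Definition 2 the interval runs backwards, and the SAP does not say how to place it.
- The adverse-event exception would catch those three rows, because its test is an end before the first double-blind dose. The consent-date sentence may have been meant to carry the same test; that is an inference.
- For the 1 March case both sentences lead to one class. A consent-date start precedes run-in, so Definition 1 gives prior to run-in. Under Definition 2, start and end both precede run-in, with the same answer. The dates differ, and the first is impossible, but the table entry does not change.

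**2. Diabetes duration.** Year known, month and day missing, diagnosis in the consent year, so the imputed date is 15 July 2018:

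- Consent 1 April: (-105 + 1)/30.4375 = -3.4 months.
- Consent 15 May: (-61 + 1)/30.4375 = -2.0 months.
- Consent 15 June: (-30 + 1)/30.4375 = -1.0 months.

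The lower limit of about -3.4 assumes that diagnosis precedes consent by at least 3 months, as the diet and exercise criterion suggests. A diagnosis in the consent year then implies consent no earlier than about 1 April.

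Share affected: let consent fall at *c* months into the year, uniform on 0 to 12, and let the true duration *d* be uniform. Both are assumptions. 15 July lies 6 + 14/31 = 6.45 months into the year. Duration is negative when 3 ≤ *d* ≤ *c* and *c* < 6.45. The area of that region is (6.45 - 3)²/2 = 5.95.

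- *d* from 3 to 36 months: 5.95/(33 × 12) = 1.5%.
- *d* from 3 to 12 months: 5.95/(9 × 12) = 5.5%.

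The day-count convention moves these by a tenth or two of a percentage point.

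At the other end, a diagnosis on 1 December 2015 with consent on 1 November 2018 has a true duration of (1066 + 1)/30.4375 = 35.1 months. With the month missing it becomes 15 July 2015 and (1205 + 1)/30.4375 = 39.6 months, beyond the 3-year limit. Under the 3 to 36 month assumption this happens when *c* > 6.45 and *d* > *c* + 24: (12 - 6.45)²/2 = 15.40, and 15.40/396 = 3.9%.

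All shares apply only to subjects whose diagnosis month is missing.

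**The case against.** The strongest reply is that nothing inferential depends on these rules, and that stands. Four stronger readings are tempting but not supported.

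- **The two sentences give opposite results.** They give different dates but the same class, prior to run-in, and assigning a class is the only permitted use.
- **Old medicines are shown as new on-treatment medicines.** For a medicine still being taken, the first-dose default is a convention that avoids missing on-treatment use. Definition 2 counts it correctly in the treatment period and loses only the earlier periods. The plain error is confined to medicines that stopped before the first double-blind dose.
- **The primary analysis is contaminated.** SAP 8.1 and its sample code contain treatment, visit, their interaction, centre and baseline HbA1c, with no duration term. Nor should imputed medicine dates trigger the rule in SAP 6.7 that sets efficacy values to missing after other antidiabetic drugs, since 6.1.2 limits them to period assignment. Protocol 9.3.2 does list disease duration in the model, while the v1.1 synopsis does not. That mismatch is a separate matter; impossible durations would enter a model only if the 9.3.2 version were run.
- **A duration under 3 months contradicts eligibility.** No criterion sets a minimum time since diagnosis. The 3-month floor is inferred from the diet and exercise requirement, and eligibility is judged at screening, not from an imputed date.

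It is also fair to say that sites must establish duration to apply the 3-year exclusion, so missing diagnosis months may be few.

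**Conclusion.** The point holds as a minor error in the SAP. Followed literally, 6.1.2 item 3 gives an impossible start date to every medicine with a completely missing start that ended on or after consent and before the first double-blind dose, and Definition 1 then puts it in the wrong period. The sentence imputing the consent date is redundant for classification and impossible as a date.

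Section 6.1 allows negative disease duration, to about -3.4 months. The shares of about 1.5% and 5.5% rest on an assumed even spread of consent dates and true durations, and apply only to subjects with a missing diagnosis month. The documents give neither the number of such subjects nor the number of medicines affected. The consequence is limited to descriptive medication and baseline tables. No test or estimate under the SAP changes.

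**What to change.** In SAP 6.1.2, start date, item 3, delete the sentence that imputes the consent date, keep the one that applies no imputation, and add: *An imputed start date is never later than the recorded end date; a medicine that ended before the first double-blind dose is classified by its end date.* In the illustration, 10 April then falls prior to run-in, and 25 April and 12 May fall in run-in.

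In SAP 6.1, add: *An imputed diagnosis date is not later than the date of informed consent and not earlier than 3 years before it.* This uses only limits that the protocol states and needs no inferred 3-month floor.

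The cost is one deletion, two added sentences and minor programming, best done before the first database lock so that no choice is left to the programmer.
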